The subject population consists of 98 participants (49 migraineurs and 49 healthy controls) who will be recruited for Part I. Participants will be of any gender and ethnicity. To ensure comparable groups, participants and controls will be matched on age (± 5 yrs), gender, and race. We have obtained IRB approval for all recruitment procedures (Wake Forest IRB protocol # IRB00027845).

Participants with migraines will be recruited through several different mechanisms 1) Wake Forest Departments of Neurology, Internal Medicine, Family Medicine and Emergency Department; 2) Wake Forest [name] Headache Research Center 3) Wake Forest Electronic Medical record system; 4) Local flyers, radio/television/newspaper advertisements. The primary source of recruitment will be through the Wake Forest Department of Neurology clinics.

The primary source of recruitment will be through the Wake Forest Department of Neurology clinics. [name] has her own headache clinic within the department, where she has seen over 300 headache patients in the last year (on average 9 new and 6 follow-up patients per week). Patients will also be recruited through the Wake Forest primary care clinics. Flyers will be placed throughout the hospital and specifically in the clinics of Neurology, Internal Medicine, OB/Gyn, and Family medicine and in the Emergency Department. On average, Wake Forest sees >800 patients/year in the Emergency Department with a diagnosis of migraine.

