Sample Size Calculation: Using the marginal benefit formula for repeated measures (Vickers),⁴⁰ and assuming an average within-person correlation between repeated measurements of 0.5, a sample size of 48/group will give us 80% power to detect an effect size as low as $d=0.62$ for the group main effect (Hypotheses 1a and 1b). Thus, if the average VAS rating in the controls is 3 (± 2 SD), we will be able to detect a VAS rating of 4.24 in migraineurs; smaller differences are unlikely to have clinical significance. For hypothesis 1c, 98 participants will also give us 84% power to detect a bivariate correlation of at least 0.4 between pain catastrophizing scores or emotional reactivity scores and pain unpleasantness levels ($r \leq 0.4$ not likely of clinical significance).

Outcomes

Stimulus-response curves will be generated for each subject using the logarithmic equation: $\log(\text{VAS pain ratings}) = \log(t - 35) * \text{coefficient} + \text{intercept}$ where t represents stimulus temperature.¹ The coefficient and intercept generated for heat pain intensity and heat pain unpleasantness will both be used as outcome variables, as well as scores from the PCS and the DERS.

Data Analyses

Statistical Analyses: We will use mixed effects hierarchical regression models with a distribution and link function appropriate to the outcome (e.g., the best fitting distribution as defined by model selection). Repeated measures within each participant (i.e., experimental trials within a session) will be handled using subject-level random effects. We do not expect missing data for this Aim, given the controlled nature of the experimental session and electronic data capture. The specific analyses are outlined for each hypothesis:

Analyses 1a: We will separately regress the individual pain outcomes (pain intensity, pain unpleasantness) on the factorial effects for group (migraine, control), stimulus (43, 45, 47, and 49 C), and repeated experimental block (1, 2, and 3). Absent any higher order two-way (e.g., group x stimulus) or three-way (e.g., group x stimulus x block) interaction involving group, we will interpret a statistically significant group main effect as evidence that the two groups differ in their experimental pain reports.

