Hypothesis 2b: MBSR will differentially affect the secondary outcome of the affective component (pain unpleasantness) of experimental heat pain compared to the education control group.

Hypothesis 2c: MBSR will improve the secondary outcomes of mindfulness, emotion regulation, pain acceptance, pain catastrophizing, and headache-related disability compared to an education control group.

Hypothesis 3A: High levels of baseline pain catastrophizing and emotional reactivity scores and high baseline levels of pain unpleasantness for experimental pain will predict the primary outcome response (migraine frequency) to MBSR.

Hypothesis 3B: Changes in mindfulness after MBSR will be directly associated with improvements in migraine frequency.

Sample Size and Randomization

Sample Size Calculation: For hypothesis 2a, using effect sizes from our pilot trial,⁵⁸ and by analyzing the data with our mixed effects hierarchical regression models, 44 participants/group (n=88) will provide >90% power with $\alpha=0.05$ to detect a difference of 1.3 migraine days/month over the course of the trial (used PASS design) (Hypothesis 2a). Hypothesis 2b has a similar power function as Part I of this study. For hypothesis 3: since hypothesis 3b is the most difficult to evaluate, this RCT is powered on this hypothesis. This calculation assumes a multivariable model examining linear changes with the four predictors (plus intercept and slope). A sample size of 88 participants will give us 80% power with effects as small as $R^2 \geq 6\%$ in the variance of the slopes; smaller predictors are unlikely to be clinically significant.¹⁰¹

Randomization: Once 4-week migraine logs are reviewed by study staff to ensure eligibility, participants will be randomized 1:1 to either MBSR or the education control group, stratified by migraine frequency (low frequency of 4-9 headaches/month or high frequency of 10-20 headaches/month). Treatment assignments will be generated by a permuted blocks method with randomly varying block size and sealed in numbered, opaque envelopes. [name] will generate the randomization (using the statistical SAS program "PROC PLAN" statement) and deliver the envelopes to the PI. Participants in both groups will continue to track their migraines with their daily REDCap logs for the duration of the trial.

Definition of Populations

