
impacted the daily probability of migraine. This effect size will be indexed by converting the daily probability to headache counts as recommended for clinical trials in headache.¹¹⁸ If necessary we will model change using polynomial trajectories (i.e., growth curves) to better fit the time-course of treatment.

Analysis 2b: To examine this hypothesis, we will conduct an ANCOVA with pain unpleasantness at post-treatment as the dependent variable, group as the independent variable, and pain unpleasantness at pre-treatment as the covariate.

Analysis 2c: This analysis is identical to 2b, with the appropriate outcomes.

Analysis 3a: Baseline levels of pain catastrophizing and emotional reactivity will be used as predictors in the multilevel models predicting the trajectory of migraine attacks over the course of treatment.

Analyses 3b: This analysis is similar to 3a, except that changes in mindfulness (i.e., change scores from pre-treatment to post-treatment) will be used as predictor of migraine trajectory.

DATA COLLECTION AND QUALITY ASSURANCE

Data Collection Forms

Information will be collected from REDCap daily headache logs for appropriate diagnosis of migraines during an initial 4 week period prior to randomization and participants will continue to track daily headaches for the duration of the trial. Ipod touches with Pendragon software will be available to those without internet access and unable to use REDCap from home. Experimental heat measurements will be conducted at baseline and at each of the 3 follow-up evaluations. Participants will also complete standardized questionnaires using REDCap at baseline and at each of the 3 follow-up evaluations with an option to complete these questionnaires at home prior to the visit. In addition, a 30 minute qualitative interview will be conducted at the first follow-up visit to evaluate the participants' experience with the interventions. Each interview will be audiotaped. Socio-demographic and clinical information will also be collected at the screening visit.

Description of data that will be recorded on human subjects. Each 30 minute qualitative interview of the migraine and control subjects will be audiotaped and then transcribed. Participants will be photographed one of the study visits. These photos will be stored on the study's secure Ishare. Each subject will have provided informed consent to perform this.

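### The 80% power stated for hypothesis 3b does not follow from its printed inputs (about 65% two-sided or 76% one-sided on the closest reading), and the Part 1 correlation power of 84% does not fit 98 participants

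*Combined protocol and SAP*

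**What the plan says.** **Part 2, Sample Size and Randomization.** Under hypothesis 3 the plan states that "since hypothesis 3b is the most difficult to evaluate, this RCT is powered on this hypothesis". It then describes the model: "This calculation assumes a multivariable model examining linear changes with the four predictors (plus intercept and slope"). The claim follows: "A sample size of 88 participants will give us 80% power with effects as small as" an R-squared of 6% in the variance of the slopes, with the remark that "smaller predictors are unlikely to be clinically significant". The four predictors are not named. An alpha of 0.05 appears in the same paragraph, but for hypothesis 2a only. For 3b there is no alpha, no sidedness, no statement of whether one predictor or all four are tested, and no figure for the variance explained by the rest of the model.

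**Part 2, hypotheses and Data Analyses.** Hypothesis 3B reads "Changes in mindfulness after MBSR will be directly associated with improvements in migraine frequency". Analyses 3b names one predictor: "changes in mindfulness (i.e., change scores from pre-treatment to post-treatment) will be used as predictor of migraine trajectory". It does not say whether both arms enter the model.

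**Part 1, Sample Size and Randomization.** For hypothesis 1c, "98 participants will also give us 84% power to detect a bivariate correlation of at least 0.4" between catastrophizing or emotional reactivity scores and unpleasantness. Part 1, Study Enrollment Procedures, gives the composition: "The subject population consists of 98 participants (49 migraineurs and 49 healthy controls) who will be recruited for Part I". The Part 1 calculation for hypotheses 1a and 1b uses 48 per group.

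**The concern.** A power statement should follow from the inputs printed beside it. For 3b, an R-squared of 6% is a small effect for 88 people, and 80% looked too high on sight. For hypothesis 1c, a correlation of 0.4 is easy to detect with 98 people, and 84% looked too low.

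The 3b figure matters because the plan rests its sample-size argument for hypothesis 3 on it and treats anything below 6% as clinically unimportant. If power at 6% is well below 80%, a non-significant mindfulness result could be read as ruling out an effect that the trial had a fair chance of missing. For hypothesis 1c the risk is different: the reader cannot tell which correlation, in which sample, is planned.

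**Working it through.** **Hypothesis 3b**

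Inputs from Part 2, Sample Size and Randomization: n = 88, four predictors, R-squared = 0.06, stated power 80%. Assumed because not printed: alpha 0.05, shown two-sided and one-sided, and q, the share of slope variance explained by the other three predictors.

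The effect is a share of between-person slope variance, so the unit is the person. Daily diary entries do not raise n above 88, and error in estimating each slope would lower power further.

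Formulas: f² = 0.06/(1 − 0.06 − q); noncentrality λ = 88 × f²; error df = 88 − 4 − 1 = 83. Power comes from the noncentral F with 1 and 83 df (two-sided) or the noncentral t with 83 df (one-sided).

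A 1-df test is the closest match, because Analyses 3b names one predictor and the sample-size text speaks of individual predictors. With q = 0, f² = 0.06/0.94 = 0.0638 and λ = 5.62:

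| q | f² | λ | Two-sided 0.05 | One-sided 0.05 |
|---|---|---|---|---|
| 0 | 0.0638 | 5.62 | 64.9% | 76.0% |
| 0.10 | 0.0714 | 6.29 | 69.8% | 80.0% |
| 0.12 | 0.0732 | 6.44 | 70.8% | 80.8% |
| 0.18 | 0.0789 | 6.95 | 74.1% | 83.4% |
| 0.28 | 0.0909 | 8.00 | 79.8% | 87.7% |

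The two-sided test reaches 80% at q = 0.283.

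Other ways of reaching the printed figure at q = 0:
- Counting 1, 5 or 6 model terms instead of 4 leaves the two-sided figure at 65%.
- Simulation with random normal predictors gives 62 to 63% two-sided and 73 to 74% one-sided.
- All 98 recruits give 69.7% two-sided and 79.9% one-sided, but the plan states 88.
- The 44 MBSR participants alone give 37% two-sided and 50% one-sided.

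Solving the other way at q = 0 with n = 88, the R-squared with 80% power is 8.4% two-sided or 6.7% one-sided. At R-squared 6%, 80% power needs 125 participants two-sided or 99 one-sided.

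**Hypothesis 1c**

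Inputs from Part 1: r = 0.4, N = 98, stated power 84%. Assumed: two-sided 0.05. Two methods:
- Fisher z: power = Φ(atanh(0.4) × √(n − 3) − 1.96), with atanh(0.4) = 0.4236.
- Single-predictor F: λ = n × 0.16/0.84, with 1 and n − 2 df.

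| n | Fisher z | F test |
|---|---|---|
| 98 | 98.5% | 99.0% |
| 49 | 81.9% | 84.9% |
| 48 | 81.1% | 84.1% |

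The F test at n = 48, the per-group size used for 1a and 1b, reproduces 84%. With n = 98, power of 84% corresponds to r of about 0.29 by either method.

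**The case against.** The strongest objection is that 65% rests on an unprinted assumption too: that the other three predictors explain none of the slope variance. The plan describes a four-predictor model and treats 6% as a minimum effect, so zero is the least favourable case. If the other predictors explained 12 to 18%, power would be 71 to 74% two-sided or 81 to 83% one-sided. This stands. The supported statement is that 80% does not follow from what is printed, with 65% (two-sided) or 76% (one-sided) as the zero-contribution case. It is not that 80% is impossible.

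A reader might prefer a joint test of all four predictors, which gives 42% at two-sided 0.05. That is not the closest reading, because Analyses 3b tests a single predictor.

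A reader might also infer that the whole trial is underpowered, since the plan says the RCT is powered on 3b. The documents do not support that. The sentence sits under hypothesis 3, which serves a secondary objective. The primary outcome, hypothesis 2a, has its own statement of more than 90% power at the same 88 participants. That statement's inputs are not fully printed, but nothing here contradicts it.

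For Part 1, it can fairly be said that understating power harms no conclusion. That is so if the correlation is pooled. It does not settle which analysis was meant, and the match at 48 per group suggests a within-group calculation.

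**Conclusion.** The point holds as a mismatch between stated power and printed inputs, in two places.

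For 3b, the printed inputs give about 65% two-sided or 76% one-sided, against 80% stated. This assumes alpha 0.05, a single-predictor test and no variance explained by the other predictors. In that two-sided case a true 6% effect would be missed about 35% of the time, not 20%. The stated 80% is recovered if the other predictors explain about 28% (two-sided) or 10% (one-sided) of slope variance, and the plan states neither condition. The figure of 88 also presumes that both arms are analysed, which the wording of hypothesis 3B leaves open.

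For hypothesis 1c, the printed N, r and power disagree: 98 to 99% at n = 98, against 84% stated. The figures fit one group of 48 or 49 (81 to 85% by method). The error is conservative if the correlation is pooled.

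Both should be corrected. Neither shows that the recruitment target is wrong.

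**What to change.** **3b.** Do one of two things:
- Restate the claim as 80% power for an R-squared of about 8.4% (one predictor, two-sided 0.05, no variance explained by the others), which is the same as about 65% power at 6%.
- Keep 6% and print the alpha, sidedness and other-predictor R-squared that yield 80%, with the reason for expecting that R-squared.

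In either case, name the four predictors, identify the one tested, and say whether both arms (88) or the MBSR arm only (44) are analysed. If only the MBSR arm, recompute the power.

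**Hypothesis 1c.** First state whether the correlation is pooled or within group. If pooled, give 98 to 99% at r = 0.4, or 84% at r of about 0.29. If within group, replace 98 with the per-group n and give the power and method for that n (84.1% by F test at 48; 82 to 85% at 49).

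**Cost.** Protocol wording only, with no extra participants or visits. Under the first option the 3b claim becomes less favourable; the second requires the sponsor to defend an assumption that is now unstated.

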Follow-up visits will occur immediately after the 8 week class is over, 3 months later and 6 months later. At each follow-up visit, participants will complete the entire instrument assessment and the QST measurements. In addition, at the first follow-up visit, participants will complete a qualitative interview.

Qualitative Interviews: At the initial follow-up, a 30-minute semi-structured interview will be conducted with participants to further explore areas not captured in our standardized quantitative measures. This will be especially important in capturing measures of treatment fidelity not already captured, especially in capturing patient/instructor interactions and enactment of treatment skills.

Reporting Procedures

Plans for ensuring necessary medical or professional intervention in the event of adverse effects to the subjects. [name] is a trained clinician and will oversee the interventions. If a medical emergency arises the appropriate steps will be taken to contact emergency services. At each study visit, the PHQ-9 survey will be scored immediately after completion by the participant. If the participant's responses suggest severe clinical depression, [name] will recommend that the participant see their primary care physician for treatment. If the participant's responses suggest active suicidal ideation, he or she will be sent directly to the emergency department.

We will promptly report any unanticipated problems, serious and unexpected adverse events, deviations or protocol changes to the IRB and Data Safety and Monitoring Board (See Data Safety and Monitoring Board for more details).

Serious adverse events (SAEs) that are unanticipated, serious, and possibly related to the study intervention will be reported to the I-DSMB, Wake Forest School of Medicine IRB, and NCCIH in accordance with requirements.

Unexpected fatal or life-threatening AEs related to the intervention will be reported to the NCCIH Program Officer within 7 days. Other serious and unexpected AEs related to the intervention will be reported to the NCCIH Program Official within 15 days.

Anticipated or unrelated SAEs will be handled in a less urgent manner but will be reported to the I-DSMB, Wake Forest School of Medicine IRB, NCCIH, and other oversight organizations in accordance with their requirements. In the annual AE summary, the I-DSMB Report will state that they have reviewed all AE reports.

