Group: A risk to taking part in this study is the likelihood of receiving an intervention (that requires time and energy) that may not be effective in helping to treat migraines. The classes or other study-related procedures may cause some, all, or none of the side effects listed below.

Most Likely

Gentle stretching can cause muscle soreness if muscles have not been exercised in a long time. Sitting for extended periods of time can be uncomfortable. Chairs will be provided for comfort, and participants will be allowed to move as needed to relieve any discomfort.

Less Likely

With any activity, there is always a risk of injury. The instructor will advise the participants to avoid any posture that causes discomfort or pain. The instructor will be attuned to watching for any problems during each session.

Rare

There have been rare case reports of meditation or yoga causing a brief limited episode of psychiatric illness. However, most of these case reports are in individuals with a prior history of unstable psychiatric illness. There are no known reports of this occurring in anyone in an MBSR class. Having a history of unstable psychiatric illness is an exclusion criteria for participating in this project so therefore we have in place an extra precaution to not encounter this risk.

Description of alternative treatments and procedures. The alternative is to not participate in the study or to refer to the personal physician for standard treatment.

STATISTICAL CONSIDERATIONS

General Design Issues

To examine the hypotheses, we will again rely on mixed effects hierarchical regression models with a distribution and link function appropriate to the outcome (e.g., binomial distribution and logit link for daily migraine probability). These models will allow us to fully utilize all of the information (i.e., rather than simply calculating change scores) by conceptualizing each diary entry as nested within a diary phase (baseline 4 weeks prior to randomization, 8 weeks of treatment, and 3 and 6 months of follow-up), within a person (random effects), who is nested within a treatment group. Missing data will be scrutinized and we will utilize sensitivity analyses and/or multiple imputation as required. The models will be conducted as described below:

Hypothesis 2a: MBSR will decrease the primary outcome of migraine frequency compared to an education control group;

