As done in prior behavioral headache research,⁶⁹ all participants who attend at least ONE class will be included in the intention-to-treat analyses. This is a modified "intent to treat" analysis that ensures exposure to the independent variable and is used and felt to be very important by behavioral scientists.

Outcomes

Our primary outcome will be change in frequency of migraine days, defined as a calendar day (00:00 to 23:59)¹⁰² when the patient reports 4 or more continuous hours of a moderate to severe headache (rating of 6-10 on 0-10 VAS pain intensity scale) and/or they treated a headache with abortive medication. Participants will track their headaches daily with REDCap logs to

demonstrate frequency, severity (both pain intensity and pain unpleasantness, as trained with QST), medications, and associated migraine symptoms (e.g., photophobia, phonophobia, nausea, vomiting). iPod Touch devices with Pendragon software will be available to those without internet access.

Secondary outcomes include changes in migraine severity (measured by pain intensity and unpleasantness on 0-10 VAS scale), migraine duration (hrs), frequency of headache days, headache duration, headache severity (measured by pain intensity and unpleasantness on 0-10 VAS scale), experimental heat pain intensity and unpleasantness (QST measurements), and changes in scores on validated measures of mindfulness, pain acceptance, pain catastrophizing, emotional reactivity, and headache-related disability compared to an education control group; determine factors that predict MBSR response on migraine pain. A headache day is defined as any day when a participant reports the presence of a headache.

We will also characterize participants before/after the intervention using measures of hope, optimism, quality of life, depression, anxiety, perceived stress, self-efficacy, sleep, fatigue, pain interference, satisfaction with participation in social roles, allodynia, and global health.

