All the secondary outcomes and additional measures will be assessed with these standardized, reliable, well-validated instruments: Five-Facet Mindfulness Questionnaire (mindfulness),^{57,103} DERS (emotion regulation),^{3,104} PCS (pain catastrophizing),^{2,36} Chronic Pain Acceptance Questionnaire (pain acceptance),¹⁰⁵ Herth Hope Index (hope),¹⁰⁶ Life Orientation Test-Revised (optimism),¹⁰⁷ Headache Impact Test-6 (HIT-6) (headache related disability),¹⁰⁸⁻¹¹⁰ Migraine Disability Assessment (MIDAS)-one month (headache related disability),^{111,112} Patient Health Questionnaire-depression module, PHQ-9 (depression),³⁴ Generalized Anxiety Disorder-7, GAD-7 (anxiety),³⁵ Headache Management Self-Efficacy Scale (self-efficacy),¹¹³ Migraine Specific Quality of Life Questionnaire, version 2.1 (MSQv2.1) (quality of life),^{114,115} the Perceived Stress Scale 10, PSS (perceived stress),¹¹⁶ the Brief Resilience Scale, the Resilience Scale for Adults, the Flourishing Scale, the Social Connectedness Scale-Revised (SCS-R), the Pittsburgh Sleep Quality Index, the Allodynia Symptom Checklist (ASC-12), and well-validated NIH Patient Reported Outcomes Measurement Information System (PROMIS) measures of sleep, fatigue, pain interference, satisfaction with participation in social roles, and global health. Changes from baseline to initial follow-up will be primary outcomes; secondary outcomes will include changes from baseline to follow-ups at 3 and 6 months.

Additional Information Collected

Sociodemographic and clinical information will be collected at the screening visit.

Expectations for improvement: Expectations can impact results.^{39,117} At baseline and after the second session, participants will rate their expectations using the Credibility/Expectancy Questionnaire.⁹⁶

Class Attendance and Home Practice: Participants in both groups will track their home activities up to the 6-month follow-up visit via REDCap logs and the instructors will track patient class attendance.

Qualitative Interviews: At the initial follow-up, a 30-minute semi-structured interview will be conducted with participants to further explore areas not captured in our standardized quantitative measures.

Data Analyses

Analysis 2a: The probability that an individual experiences a migraine on any given day will be examined as a function of group (MBSR vs. control) and treatment phase. A statistically significant group x phase interaction will be interpreted as evidence that treatment differentially

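### The primary analysis (2a) decides a directional hypothesis by any significant group by phase interaction, with no period, contrast or direction named for migraine days

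*Combined protocol and SAP*

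**What the plan says.** All places are in Part 2.

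- **General Design Issues.** Diary entries are nested in phases: "baseline 4 weeks prior to randomization, 8 weeks of treatment, and 3 and 6 months of follow-up". Hypothesis 2a, stated in the same section, is directional: a decrease against the education control.
- **Data Analyses, Analysis 2a.** Daily migraine probability is modelled by group and phase. The decision rule is: "A statistically significant group x phase interaction will be interpreted as evidence that treatment differentially" changed that probability. The effect is then converted to headache counts. The section adds: "If necessary we will model change using polynomial trajectories", to fit the time course better. It gives no criterion for when, no degree, and no statement of which test would then decide.
- **Outcomes.** "Our primary outcome will be change in frequency of migraine days". No period is attached. A later paragraph opens "All the secondary outcomes and additional measures will be assessed with these standardized, reliable, well-validated instruments", lists questionnaires, and closes: "Changes from baseline to initial follow-up will be primary outcomes; secondary outcomes will include changes from baseline to follow-ups at 3 and 6 months".
- **Follow-up Visits.** "Follow-up visits will occur immediately after the 8 week class is over, 3 months later and 6 months later". No diary phase carries the name initial follow-up.
- **Sample Size and Randomization.** With 44 per group and alpha 0.05, power is put above 90% for 1.3 migraine days per month, a difference described as spanning the whole trial.

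**The concern.** A group by phase interaction asks whether the group difference is the same in every phase. It does not ask whether MBSR lowered migraine days in a given period. Followed literally, the rule lets the primary claim rest on a late phase, on opposing differences in different phases, or on a difference that favours control. A reader of the result could not tell in advance which estimate was meant to decide the trial. The open option of growth curves leaves the form of the deciding test unfixed as well. By contrast, Analysis 2b, for a secondary outcome, specifies one baseline-adjusted post-treatment group comparison.

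**Working it through.** **1. The plan's own figure.** Inputs: 44 per group, 1.3 days, alpha 0.05 (two-sided assumed), and the pilot result in Table 4 (−1.4 per month, d = 0.32, 95% CI −4.6 to 1.8, n = 10 and 9).

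- SD from d: 1.4/0.32 = 4.375.
- SD from the CI: half-width 3.2; 3.2/2.110 (t, 17 df) = 1.517; 1.517/√(1/10 + 1/9) = 3.30.
- Two-sample power, Φ(1.3/(SD·√(2/44)) − 1.96): 28.6% with SD 4.375 and 45.5% with SD 3.30. Power of 90% needs an SD of 1.88.
- With repeated measures and baseline adjustment, the variance multiplier is (1 + (k−1)r)/k − r². For SD 3.30, k = 3 and r = 0.7 it is 0.80 − 0.49 = 0.31, which gives 91%.

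So more than 90% is reachable, but only with an SD, a correlation and a number of measures that the plan does not state. The figure can be neither reproduced nor refuted, and it cannot be tied to a particular contrast.

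**2. Degrees of freedom.** Read as four phases: (2−1)(4−1) = 3. With follow-up as one phase: (2−1)(3−1) = 2. The plan gives no count, but the test has more than 1 df either way.

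**3. What the rule responds to.** Let δ be the group difference in each phase, in the order baseline, treatment, 3 months, 6 months. Assume equal precision per phase, compound symmetry, and a large-sample Wald test. With c a common variance factor, the noncentralities are:

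- baseline-to-treatment contrast, 1 df: (δ₁ − δ₀)²/(2c);
- baseline to the mean of the later phases, 1 df: (mean of δ₁ to δ₃ − δ₀)²/(4c/3);
- interaction, 3 df: Σ(δⱼ − δ̄)²/c.

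Setting the first to 10.51 (90% power) for δ₁ = 1 gives 1/c = 21.01.

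| Pattern δ | Σ(δⱼ − δ̄)² | Interaction, 3 df | Baseline to treatment | Baseline to later mean |
|---|---|---|---|---|
| Sustained (0,1,1,1) | 0.75 | 15.76: 93.0% | 90% | 15.76: 97.8% |
| Treatment only (0,1,0,0) | 0.75 | 15.76: 93.0% | 90% | 1.75: 26.3% |
| Last only (0,0,0,1) | 0.75 | 15.76: 93.0% | 5% | 1.75: 26.3% |
| Halved later (0,1,½,½) | 0.50 | 10.51: 78.4% | 90% | not needed |

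Under AR(1) with r = 0.5 to 0.7, the interaction test has 83% to 80% for last only, the same range for sustained, and 95% to 96% for treatment only. With three phases (2 df), last only gives 92.8% under compound symmetry and 86% to 84% under AR(1). The interaction noncentrality is built from squares, so a pattern of the same size favouring control rejects equally often.

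**4. Power at equal noncentrality.** Holding 10.51 fixed, power is 90% on 1 df, 83.5% on 2 df and 78.4% on 3 df. Holding 7.85 fixed, 80% becomes 64.5% on 3 df. Step 3 shows that this is a special case: the noncentrality is not normally equal, because the interaction also draws on the other phases.

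**5. Open model choice.** As an illustration, suppose any of the 3-df phase test, a linear test or a quadratic test could count as success. With phase midpoints assumed at 0, 1.5, 4 and 6.5 months, simulated type I error is about 9.2% instead of 5%. The plan does not say that it would work this way. It simply does not exclude it.

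**The case against.** The fair defence is that 2a is coherent as a whole-trial analysis. General Design Issues says that the models exploit all diary information, and the power statement spans the whole trial. The sentence that makes change to initial follow-up primary closes a paragraph on secondary outcomes and questionnaires. A reader might infer that the plan contradicts its own stated primary period. The documents do not establish that, because the sentence need not apply to migraine days. This part of the defence stands.

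It does not rescue the rule. If the whole trial is meant, the matching test is baseline against the average of the later phases. Step 3 shows that the interaction differs sharply from it: 93.0% against 26.3% when the effect is in the last phase only.

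On direction, Hypothesis 2a is worded as a decrease, and the conversion to headache counts would show the sign. An honest report of a result favouring control could not claim support for 2a. That softens the point, but the decision rule still carries no sign.

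On the polynomials, the text says that they serve fit. It does not say that they replace the interaction test or are chosen after the results are seen. Only the missing trigger and the missing statement of which test decides are established.

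**Conclusion.** The point holds as a defect in the primary decision rule. It names no period, contrast or direction, and the rest of the plan does not supply them for migraine days. The size is the gap in step 3: 80% to 93% rejection for a last-phase-only effect, against 5% for the baseline-to-treatment contrast. This assumes four phases of equal precision and the correlations shown. With three phases it is 84% to 93%.

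Two further readings should be resisted. One is that the interaction test generally costs power. It has 93% for a sustained or treatment-only effect under compound symmetry and 95% to 96% for treatment-only under AR(1), but 80% to 83% for sustained under AR(1). The fall from 90% to 78% holds only at equal noncentrality. The other is that the stated power above 90% is wrong. Its inputs are not given, so all that can be said is that it is not tied to a defined test.

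This should be settled before diary data are analysed by arm, because it governs the trial's main claim.

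**What to change.** 1. Name one diary window against the 4-week baseline as the primary period for migraine days, and reconcile General Design Issues, Sample Size and Outcomes with it. One example is a window ending at the initial follow-up visit. Its length must be stated: that visit comes straight after the classes, so a 4-week window would cover class weeks 5 to 8. If the sponsor means the whole trial, baseline against the average of the later phases is also a single contrast.
2. Test that window as one 1-df group contrast from the same mixed model. Success requires significance and a difference in favour of MBSR. Report it in migraine days per 28 days with a 95% CI.
3. Make the other phase contrasts secondary and the polynomial trajectories exploratory.
4. Restate power for the chosen contrast, with its SD and within-person correlation.

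The cost is SAP wording and a fresh power statement. The data, visits and model family stay the same. The downside is that an effect outside the chosen window becomes a secondary finding.
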